6.1 Inclusion Criteria

- I. Patients aged 5-15 years of age, with consent from and attendance / guidance by parent or guardian
- II. Patients aged 16 years and over
- III. Able and willing to sign written Informed Consent
- IV. Interest in participating in the study
- V. Known history / diagnosis of Sickle Cell Disease

6.2 Exclusion Criteria

- I. Incapacity to provide informed written consent
- II. Known allergic reaction to any materials in wearable device

7. Pre-Focus Group Surveys and Focus Group Interactive Forms

Patients who enrol to participate within the focus groups will be sent a pre-focus group survey through which to record basic background information around their interest in technology as part of their care, to be self-administered by each patient and with multiple choice questions including:

1. *Do you own a wearable device, e.g. a smart watch? If so, which device do you currently own?*
2. *If owned, how often do you use a wearable device?*
3. *What are your biggest hesitations around wearable technology?*
4. *Which wearable device would you be most interested in using?*
5. *What features would you most wish for your wearable to have?*
6. *Would you be more inclined to use a wearable if it included healthcare features?*
7. *Would you want to link your wearable to a smartphone app?*

During the focus group sessions themselves, patients will be asked to participate in an interactive survey that follows the structure of the session and is guided by the group facilitator, outlined in Section 4.4. All answers remain anonymised and non-identifiable, intended solely to understand experiences and feelings around SCD and the impact of technology from a patient-perspective among the group as a whole. Both the pre-focus group survey and interactive focus group forms will be hosted on Typeform, which provides the platform for a patient friendly survey under full GDPR (General Data Protection Regulation) compliance.

7.1 Patient Numbering

A patient number uniquely identifies each patient in the study; this is a combination of their treatment centre number and participant number. Upon signing the informed consent form, the patient will be assigned a patient number by a health professional at their centre, which they have to enter when they log into the focus group interactive forms.

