No patient wishes to attend A&E, but may be left in a situation where they are signposted from day units without any certainty that it is truly an A&E situation, solely due to a lack of capacity. For clinicians specialising in SCD, ED is certainly not the preferred route for handling issues such as pain management, as these are not specialised units and face large patient volumes as standard, with staff often unfamiliar with the disease and substantial delays for patients in receiving the treatment they need. Previous studies have shown the benefits of providing ambulatory care and avoiding admission to A&E in improving patient outcomes, providing those who need it with the treatment they need to get their pain under control and return home quickly and safely, therefore highlighting a significant need for processes which ensure patients are able to receive the appropriate care in the correct environment.

[figure not shown]

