3.1 Primary Aim

The primary aim is to study the continuous pattern of vital parameters, collected over a long duration, within a sample cohort of consenting patients with SCD in order to determine how these relate to acute and chronic illnesses, as well as healthcare utilisation.

This will be through the creation of a unified data platform – comprising historical patient data, a full genetic background, and real-time patient data – through the incorporation of a wearable device into patient disease management.

Through this, the intended outcome will be improved quality and duration of life in patients.

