4 Post-Study Focus Groups Sessions with participating patients to gather feedback from the pilot and outline next steps accordingly							

6. Population

Any patient with a diagnosis of SCD, or child under 16 years of age with parental guidance, will be eligible to participate in the digital data platform / wearable pilot and focus group studies.

Patients will be recruited through multiple channels in order to ensure the involvement of as large and heterogeneous a patient cohort as possible. For these initial focus groups and digital data platform / wearable pilot trial, this recruitment will therefore be through the Sickle Cell Society's patient network, as well as patients treated at the hospitals of London North West University Healthcare NHS Trust and Barts Health NHS Trust. Estimates from the National Haemoglobinopathy Registry suggest a potential patient cohort of 1,324 patients at Barts Health NHS Trust, and an additional 418 patients at London North West University Healthcare NHS Trust. It is hoped that a greater number of patients outside of the London region will also be included via the Sickle Cell Society, and that the trial will be expanded to include additional treatment centres with time.

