7.2 Patient Withdrawal

Patients may voluntarily withdraw from the study at any time, as protected by GDPR, or be dropped from it at the discretion of the responsible clinician (investigator) at the NHS Trust. Patients may be withdrawn from the study if any of the following occur:

Patient or parent withdrew consent

Lost to follow-up

Death

Administrative problems

For patients who are lost to follow-up, the investigator will show 'due diligence' by documenting steps taken to contact the patient, such as dates of telephone calls, and mailings.

8. Statistical Analyses

An initial high-level investigation using descriptive analysis will be conducted across all variables in order to identify key trends and insights, from which further correlations and statistical significance will be tested. This will predominantly be performed using IBM SPSS Statistics 24 and Microsoft Excel, collected data analysed for outliers through Boxplot and Q-Q Plots, for normal distribution using Shapiro-Wilks testing, and for homogeneity of variance using Levene's testing. Due to the exploratory nature of the study, hierarchical stepwise regression of the outlined data points (Section 4.2 & 4.3) will be conducted, and any outliers detected through assumption testing will not be immediately excluded from analyses, instead further investigated to identify any clinically significant causes. For data that do not violate these assumptions, either independent t-tests (for experiments with two experimental groups) or one-way ANOVA (for experimental groups of 3 or more) will be performed, with Bonferroni post-hoc testing. Those that do violate these assumptions will undergo non-parametric Kruskal-Wallis testing. Each analysis will be based upon demographic variables, such as age and gender, correlated against genetic and clinical variables including hospital admissions, comorbidities, genotype, phenotype, and wearables collected data (Section 4.3). Those with p-values below 0.05 will be considered as statistically significant and undergo further study.

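### Section 8 gives treatment centre no place in between-patient analyses of hospital use, although the centre is coded in every patient number, so differences between centres can pass for patient-level associations

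*Protocol*

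**What the plan says.** - **Aim.** Protocol 3.1 sets out to study vital parameters over time and "determine how these relate to acute and chronic illnesses, as well as healthcare utilisation".
- **Access to care.** Protocol 1.3 describes patients being "signposted from day units without any certainty that it is truly an A&E situation, solely due to a lack of capacity". The same section mentions limited day-unit availability even at large centres. Section 2.2 returns to poor day-unit access and refers to the capacity of trusts.
- **Recruitment.** Protocol 6: "Estimates from the National Haemoglobinopathy Registry suggest a potential patient cohort of 1,324 patients at Barts Health NHS Trust", with another 418 at the second trust. The Sickle Cell Society is a further route, and more centres are expected later.
- **Centre identifier.** Protocol 7.1, on the patient number: "this is a combination of their treatment centre number and participant number". The rule stands among the focus-group sections but covers each patient in the study.
- **Analysis.** Protocol 8 names "demographic variables, such as age and gender, correlated against genetic and clinical variables including hospital admissions, comorbidities, genotype, phenotype" and the wearables data. It states that "hierarchical stepwise regression of the outlined data points (Section 4.2 & 4.3) will be conducted". For group comparisons, "either independent t-tests (for experiments with two experimental groups) or one-way ANOVA (for experimental groups of 3 or more) will be performed", with Kruskal-Wallis where assumptions fail. Longitudinal data go to a two-way repeated measures ANOVA. Centre is named in none of these, and Sections 4.2 and 4.3 do not list it.

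**The concern.** The protocol identifies a cause of hospital use that lies in the service and not in the patient. Suppose one centre records more admissions for equally ill patients and also treats a different mix by age, genotype or severity. Heart rate, activity or genotype would then correlate with admissions across the pooled cohort with no such relation inside any centre.

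The t-test, one-way ANOVA and Kruskal-Wallis test each take one factor. When they compare patient groups they cannot also hold a centre term, so an analysis plan that follows Section 8 as written could not adjust those comparisons. The regression could hold one, but stepwise selection could drop it again.

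Under Section 8, results with p below 0.05 go on to further study, and the platform's predictive algorithms build on the associations found. A centre artefact could travel that far.

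**Working it through.** **Inputs from the protocol**

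- Sample size 300 (4.1). The protocol's figure reproduces: 0.02 × 15,000 = 300. At the lower population bound it would be 0.02 × 12,500 = 250. This is a recruitment share, not a power calculation, and serves here only as n.
- Trust pools 1,324 and 418 (6). Share p = 1,324 / (1,324 + 418) = 1,324 / 1,742 = 0.760. Of 300 patients that is 228 and 72, if enrolment followed the pools and only these two centres contributed.
- Threshold p < 0.05 (8), taken as two-sided because no side is stated.

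**Inputs assumed, because the documents give none**

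- dx: difference between centres in the mean of the metric, in within-centre SDs, 0 to 0.8.
- Difference between centres in hospital use: dy = 0.2 to 0.8 SD, or an admission rate ratio of 1 to 2.
- For simulated counts: mean 1.5 admissions, negative binomial with gamma shape 0.8.
- No association within either centre.

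**Step 1: correlation produced by centre alone**

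With v = p(1 − p) = 0.760 × 0.240 = 0.182,

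r = v·dx·dy / √[(1 + v·dx²)(1 + v·dy²)].

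The rejection probability follows from Fisher's z: δ = atanh(r) × √297, and P = Φ(δ − 1.96) + Φ(−δ − 1.96).

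Example, dx = 0.5 and dy = 0.8: r = 0.182 × 0.4 / √(1.046 × 1.117) = 0.0675; δ = 1.165; P = 0.214.

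| dx | dy | r | P(reject) |
|---|---|---|---|
| 0 | 0.8 | 0 | 5.0% |
| 0.2 | 0.2 | 0.007 | 5.2% |
| 0.3 | 0.5 | 0.027 | 7.4% |
| 0.5 | 0.5 | 0.044 | 11.7% |
| 0.5 | 0.8 | 0.068 | 21.4% |

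**Step 2: simulation with count data**

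4,000 runs per cell; log(1 + admissions) correlated with the metric, without and then with adjustment for centre. False-positive rates:

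| Rate ratio | dx | Without centre | With centre |
|---|---|---|---|
| 1 | 0.5 | 5.3% | 5.1% |
| 1.5 | 0.3 | 5.2% | 4.8% |
| 1.5 | 0.5 | 7.2% | 4.7% |
| 1.5 | 0.8 | 10.4% | 4.9% |
| 2 | 0 | 4.6% | 4.6% |
| 2 | 0.5 | 11.8% | 4.7% |
| 2 | 0.8 | 23.6% | 4.4% |

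Over all cells, adjusted rates lie between 4.3% and 5.8%. When centres differ in only one of the two variables, the unadjusted rate stays near 5%.

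A separate simulation with rank tests, 2- to 3-fold differences in admissions and 5 to 8 bpm differences in mean heart rate (SD 12, so 0.42 to 0.67 SD) gave 9% to 27% without centre and 4% to 6% with it. The upper end depends on the test and the assumed counts, so read it as an order of size.

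**The case against.** **Choice of covariates belongs in the analysis plan.** Largely fair for the regression. The variable lists in Section 8 are open-ended, and a plan not shown here could add a centre block. A reader might infer that the sponsor decided to leave centre out; the protocol is only silent. What survives is that the protocol itself fixes one-factor tests, which cannot carry centre as a stratum, and a stepwise procedure that need not keep it. The same tests also omit every other covariate, so the limit is general. Centre is singled out because the protocol itself describes capacity as affecting where patients are treated.

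**No passage says the centres differ.** Correct. Sections 1.3 and 2.2 describe a general shortage, and mainly the choice between day unit and A&E rather than admission counts. A reader might infer that the two trusts differ in capacity or case mix and that utilisation results will therefore be biased. The documents do not support that: bias needs centres to differ in both hospital use and the predictor, and neither difference is stated.

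**The simulated setting is simplified.** It uses two centres in proportion to potential pools, not enrolment, and omits Society recruits treated elsewhere. That stands as a limit on the figures, not on the mechanism.

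**Much of the design is within patients.** Section 4.5.2 makes each patient's own monitored baseline the comparison. A patient's fixed centre cannot confound change within that patient. This stands and restricts the point to between-patient analyses.

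**The study is exploratory.** It is, and a p-value only prompts further study. That argues for a modest grade, not for leaving out a variable already held.

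**Conclusion.** The point holds for between-patient analyses with a utilisation outcome: as written, Section 8 allows a difference between centres to appear as a patient-level association. Whether it will do so cannot be told from the documents. Under the assumed differences, the nominal 5% per test ranges from about 5% to about 25%, and inflation is slight unless centres differ substantially in both variables. Adjustment brings the rate back to about 5% in every scenario examined. This is a worthwhile, cheap improvement and not a flaw that invalidates the study.

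**What to change.** For between-patient analyses in which admissions, A&E attendance or other hospital use is the outcome:

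1. Define centre as the place of treatment, taken from the patient number and not from the recruitment route. A Society recruit treated at one of the two trusts belongs to that trust.
2. Force centre into the first block of the hierarchical regression, exempt from stepwise removal. Pool only centres with few patients, or use a random centre effect as centres are added.
3. For group comparisons, use a centre-stratified rank test (van Elteren for two groups, its stratified Kruskal-Wallis extension for three or more) or a two-factor model with centre.
4. Show the estimates by centre beside the pooled one, so that readers can see whether centre matters.

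The cost is one degree of freedom per extra centre, slightly more analysis and a few sentences of text. No new data are needed, provided that the centre number of Society recruits denotes where they are treated. Within-patient analyses stay as they are.

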7.2 Patient Withdrawal

Patients may voluntarily withdraw from the study at any time, as protected by GDPR, or be dropped from it at the discretion of the responsible clinician (investigator) at the NHS Trust. Patients may be withdrawn from the study if any of the following occur:

Patient or parent withdrew consent

Lost to follow-up

Death

Administrative problems

For patients who are lost to follow-up, the investigator will show 'due diligence' by documenting steps taken to contact the patient, such as dates of telephone calls, and mailings.

8. Statistical Analyses

An initial high-level investigation using descriptive analysis will be conducted across all variables in order to identify key trends and insights, from which further correlations and statistical significance will be tested. This will predominantly be performed using IBM SPSS Statistics 24 and Microsoft Excel, collected data analysed for outliers through Boxplot and Q-Q Plots, for normal distribution using Shapiro-Wilks testing, and for homogeneity of variance using Levene's testing. Due to the exploratory nature of the study, hierarchical stepwise regression of the outlined data points (Section 4.2 & 4.3) will be conducted, and any outliers detected through assumption testing will not be immediately excluded from analyses, instead further investigated to identify any clinically significant causes. For data that do not violate these assumptions, either independent t-tests (for experiments with two experimental groups) or one-way ANOVA (for experimental groups of 3 or more) will be performed, with Bonferroni post-hoc testing. Those that do violate these assumptions will undergo non-parametric Kruskal-Wallis testing. Each analysis will be based upon demographic variables, such as age and gender, correlated against genetic and clinical variables including hospital admissions, comorbidities, genotype, phenotype, and wearables collected data (Section 4.3). Those with p-values below 0.05 will be considered as statistically significant and undergo further study.

An additional focus for the study regards data collected over extended periods of time and the progression of the disease state over this period, therefore requiring the inclusion of two independent variables. For such data, this will require Mauchly's test for sphericity in addition to Shapiro-Wilks testing for normal distribution. These data will then be tested for statistical significance using a two-way repeated measures ANOVA with a Bonferroni adjustment. Each step of the analytical output will be reported alongside changes in variance and F change, and collinearity of the independent variables will be investigated within the regression model.

This statistical analysis will in part feed into and be supported by the data platform's advanced AI and ML algorithms. However, the primary purpose of the AI technology will revolve around the predictive element of this study, highlighting potential outcomes and suggestions for optimal treatment pathways based upon the statistical analysis conducted, and key trends or associations identified.

9. Administrative Procedures

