3.2 Secondary Aim

A secondary aim is to further develop the features and usability of the data platform and wearable device through a patient lens, in an ancillary study with patient focus groups around 3 key research areas: SCD's impact on psychological wellbeing, the usefulness of wearables in day-to-day patient life, and concerns around consenting to data sharing.

4. Project Design

[figure not shown]
The project will be a combination of focus groups and data collection. This will be an ongoing, data-driven project, revolving around the collation of episodic and live data points including admission, diagnostic, pathology, radiology, primary care, pharmacy, physiotherapy, Hospital Episode Statistics (HES), Open Data, clinical data points, and the incorporation of live wearable device data. Cultivation of the most relevant data points in the context of SCD has been ongoing with the support of expert clinicians in the field, and will be further developed through the input of patients themselves during a series of patient focus groups, in order to establish what the most important factors are to SCD care through a patient-lens. Wearable devices will be provided to patients who do not already own one, in support of the unified digital data platform, within a pilot study with consenting patients who choose to register following these patient focus groups, as well as those who have enrolled through the Sickle Cell Society and from patient cohorts at treatment centres such as London North West University Healthcare NHS Trust and Barts Health NHS Trust. The project's development will further be supported through the inclusion of a number of focus groups between specialist doctors and nurses, as well as healthcare managers, public health officials and commissioners.

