4.1 Sample Size

There is an estimated 12,500-15,000 people living with SCD in the UK^{xvii}. Our patient sample size is based upon an estimated minimum proportion of the total population of patients with SCD we aim to enrol onto the digital platform and wearables pilot study, assuming not all patients will be reached by the initial programme launch through the Sickle Cell Society and partnering trusts, and that of those who are, not all will provide consent or be interested in participating. As such, our starting goal is to recruit 2% of the total UK SCD patient population, at 300 patients.

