4.5.2 Digital Data Platform and Wearables Pilot

Patients who enrol onto the pilot trial, either as a follow on from the patient focus groups or through recruitment via the Sickle Cell Society, London North West University Healthcare NHS Trust, or Barts Health NHS Trust, will be able to use either their own existing device or will be provided with a comparable market available smartwatch by the study. Data points, as summarised in Section 4.3, will be collected in an automated fashion on an ongoing basis, before transmission to a secure cloud database. This provides a novel approach to the monitoring of SCD that forgoes the need for patients to manually record information themselves and provides the potential for a larger patient cohort through remote monitoring, collecting a greater wealth of more in-depth, real-time and longitudinal data from patients during their daily lives. This supports a higher degree of compliance through decreased intrusion and an improved quality of data through improved objectivity and the elimination of retrospective recall. Furthermore, the utilisation of a wearable device provides the establishing of a baseline identified by 24/7 monitoring of data collection, providing a precise comparison for any patterns and changes over time to inform improved treatment pathways.

Patients will be set up with an electronic account and access to the digital platform through which their personal data can be accessed and visualised, and any additional metrics – such as body weight, dietary intake, emotional wellbeing, and additional medication consumption – can be manually input by the patient themselves as desired.

5. Project Plan

As part of the process of engaging patients prior to the full study and technology pilot trial, the project entails a series of initial pre-study patient focus groups over a 2-month period, in order to gather the relevant insights to ensure the study design, steps and outcomes are curated around a patient-centric outlook. Our intended timetable is as follows:

Project Stage	2 months	3 months	12 months				1 month
1 Pre-Study Focus Groups Engaging patients in study development prior to initiation of the full wearable pilot							
2 Pilot Study Enrolment Patients recruited to participate in the pilot through pre-study focus groups, the Sickle Cell Society & participating trusts							
3 Wearables Pilot Study Trialling of the live wearable and digital platform with patients, data collection, and analysis							

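### Section 8 applies independence-based regression and group tests to wearable and hospital data that repeat within each patient, without fixing the unit of analysis or allowing for within-patient correlation

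*Protocol*

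**What the plan says.** Protocol Section 8 (Statistical Analyses) states that "hierarchical stepwise regression of the outlined data points (Section 4.2 & 4.3) will be conducted". Where the assumption checks pass, "either independent t-tests (for experiments with two experimental groups) or one-way ANOVA (for experimental groups of 3 or more) will be performed". Where they fail, Kruskal-Wallis is used. Section 8 then says that each analysis sets demographic variables against genetic and clinical ones, and it lists hospital admissions and the Section 4.3 wearable data among them. The decision rule is: "Those with p-values below 0.05 will be considered as statistically significant and undergo further study".

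The inputs repeat within a patient. Section 4 (Project Design) describes the "collation of episodic and live data points", and Section 4.5.2 says the Section 4.3 data points "will be collected in an automated fashion on an ongoing basis", with round-the-clock monitoring. The timetable in Section 5 gives the wearables pilot 12 months.

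The checks named for these methods cover outliers, normality and equal variance. Independence of rows is not among them. No per-patient summary, patient effect or clustered standard error is mentioned for the regression or the group tests.

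A later paragraph of Section 8 takes up, as an additional focus, data gathered over long periods and disease progression. It assigns these to a two-way repeated measures ANOVA with Mauchly's test, and then returns to the regression: "Each step of the analytical output will be reported alongside changes in variance and F change". Reporting F change step by step shows that hierarchical means entering predictors in blocks. It does not mean a multilevel model.

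**The concern.** Stepwise regression, the independent t-test, one-way ANOVA and Kruskal-Wallis all take their reference distribution from independent rows. Readings from one patient are alike: a person with a high resting heart rate tends to have one throughout the year. If readings are entered as rows, ordinary differences between patients can look like an effect of gender, genotype or any other patient-level factor, because the test counts far more information than the patients supply. This is separate from testing many variables. One pre-chosen test would already be miscalibrated, and a Bonferroni adjustment would not repair it.

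The other reading, one value per patient, is valid on this point but loses part of the question. Section 3.1 asks how the continuous pattern of vital signs relates to acute and chronic illness and healthcare use, and Section 2.1 wants metrics that signal an approaching crisis. Those are largely questions about change within a patient.

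The results carry weight. Associations below 0.05 go forward to further study, and Section 8 bases the platform's predicted outcomes and treatment-pathway suggestions on the statistical analysis.

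**Working it through.** **The plan's own figure.** Section 4.1 states "There is an estimated 12,500-15,000 people living with SCD in the UK" and "our starting goal is to recruit 2% of the total UK SCD patient population, at 300 patients". 0.02 × 15,000 = 300, so the figure is reproduced at the upper end of the range (0.02 × 12,500 = 250 at the lower end). It is a recruitment target and not a power calculation. The formula for the inflation below does not involve the number of patients.

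**Inputs.** The nominal level is 0.05 (Section 8), taken as two-sided because the side is not stated. The number of patients is 300 (Section 4.1). The protocol gives neither the rows per patient, m, nor the ICC, so both are assumed: m = 12, 52 or 365 (monthly, weekly or daily rows over the 12-month pilot) and ICC from 0.05 to 0.7.

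**Test of a patient-level factor on pooled rows.** The design effect is DE = 1 + (m − 1) × ICC. The actual two-sided error is 2 × [1 − Φ(1.96/√DE)].

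Example with m = 12 and ICC = 0.5: DE = 1 + 11 × 0.5 = 6.5; 1.96/√6.5 = 0.769; error = 0.442.

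| ICC | m = 1 | m = 12 | m = 52 | m = 365 |
|---|---|---|---|---|
| 0.05 | 0.05 | 0.115 | 0.298 | 0.655 |
| 0.2 | 0.05 | 0.273 | 0.558 | 0.820 |
| 0.3 | 0.05 | 0.345 | 0.627 | 0.852 |
| 0.5 | 0.05 | 0.442 | 0.703 | 0.885 |
| 0.7 | 0.05 | 0.506 | 0.746 | 0.902 |

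**Simulation check** (300 patients, no true difference, 2,000 runs for the t-test and 1,000 for three groups):
- Pooled t-test, 150 against 150: 0.34 (ICC 0.3, m = 12), 0.45 (ICC 0.5, m = 12) and 0.73 (ICC 0.5, m = 52).
- Three groups, ICC 0.3, m = 12: ANOVA 0.52, Kruskal-Wallis 0.51.
- t-test on one mean per patient: 0.046 to 0.057 in every scenario.

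**Regression of one repeated metric on another, unrelated one.** Here DE is approximately 1 + (m − 1) × ICCx × ICCy.
- Both ICC 0.3, m = 12: DE = 1 + 11 × 0.09 = 1.99, error 0.165; simulated 0.17.
- ICC 0.5 and 0.3, m = 52: DE = 1 + 51 × 0.15 = 8.65, error 0.505; simulated 0.50.
- Both ICC 0.5, m = 52: DE = 1 + 51 × 0.25 = 13.75, error 0.597; simulated 0.60.
- Predictor with ICC 0, m = 52: DE = 1, error 0.05; simulated 0.04.

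The regression is therefore inflated when both metrics differ between patients. It is not inflated for a predictor that varies only within patients. These results assume the same correlation between any two readings of a patient.

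**The case against.** Four objections deserve an answer.

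- **The unit is never stated.** A reader might infer that Section 8 does run its tests on individual readings. The protocol does not say so. The passages on ongoing and episodic collection describe how data are gathered, not how they enter a model. Gender, genotype and comorbidity have one value per patient, and admissions can be a per-patient count. This objection stands, so the inflation is conditional. It does not clear the plan, because the one-value reading leaves the acute-illness part of the aim without a method in the regression and group tests.
- **Repeated measures are provided for.** A reader might infer that Section 8 ignores repetition altogether. It does not: the repeated measures ANOVA accounts for within-patient correlation, and a generous reading could send the wearable series there. But Section 8 also names wearable data in its independent-samples analyses, draws no boundary between the two routes, and leaves the regression outside the repeated measures provision.
- **Such detail belongs in a statistical analysis plan.** The choice of summary or model often does. Here the protocol itself names the tests and the data they take, so a plan that follows it inherits the problem.
- **The study is exploratory.** Section 8 says so, and no confirmatory hypothesis is stated. That lowers the severity, but a p-value used to select findings should still be calibrated.

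**Conclusion.** The point holds in conditional form. Section 8 applies independence-based methods to data that repeat within patients, without fixing the unit of analysis or allowing for within-patient correlation, and its repeated measures ANOVA does not cover the regression.

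If rows are readings or episodes, a nominal 5% test of a patient-level factor has an actual error of about 11% at ICC 0.05 and 27 to 51% at ICC 0.2 to 0.7 with 12 rows per patient, and more with more rows. Tests between two metrics are inflated when both vary between patients. If each patient supplies one value, the error is about 5%, and the cost is the unanswered within-patient question.

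Two stronger conclusions are not supported. Not every standard error is too small, because a predictor varying only within patients showed no inflation. And the larger figures for weekly or daily rows do not predict this study's error rate: the ICCs and row counts are assumptions, and the protocol nowhere plans to pool daily rows. In a self-described exploratory study this should be fixed, but it does not invalidate the study.

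**What to change.** In Section 8, state the unit for each type of question and match the method to it.

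- **Patient-level questions** (for example gender, genotype or comorbidity): reduce each wearable or episodic metric to one summary per patient before any t-test, ANOVA, Kruskal-Wallis test or regression.
- **Reading-, day- or episode-level questions** (for example vital signs against crises or admissions): replace the ordinary regression with a mixed model with a patient random intercept, or with GEE using patient-clustered robust standard errors.
- **Repeated measures ANOVA:** say which data go to it and which to the methods above.

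Splitting each metric into the patient's own mean and the deviation from it is optional. It would separate differences between patients from changes within them.

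The cost is protocol wording and modest extra programming. No new data or patients are needed. Intervals will be wider and fewer results will fall below 0.05.
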